9.3.3 Covariates

Variable	Description	
Demographic and socioeconomic characteristics		
Age	Age as of index date in whole years will be calculated based on the difference between the patient's birth date and index date.	
Women	Women will be a binary indicator for whether the beneficiary was woman as indicated on the enrollment record covering the index date.	
Census region	Census region will be a categorical variable defined by categorizing the beneficiary's state of residence into Census regions (Northeast, South, Midwest, West) from the enrollment record covering the index date	
Index year	Index year will be a categorical variable defined as the year of the index date and will take the values 2014, 2015 2016, 2017, 2018, 2019, 2020 or 2021.	
Clinical characteristics		
Charlson Comorbidity Index (CCI)	Charlson Comorbidity Index (CCI) during pre- index period: A CCI score will be calculated for each patient using diagnosis codes on medical claims during the pre-index period. The CCI was developed in 1987 based on 1-year mortality data	

NIS Protocol Page 20 of 36

Variable	Description
	from internal medicine patients, and encompasses 19 medical conditions weighted 1–6 with total scores ranging from 0–37 (Charlson ME 1987). For this study, CCI adapted for use with both ICD-9-CM and ICD-10 codes will be used (Quan H 2005). The CCI will be reported as both a continuous measure and a categorical measure (0=low, 1-2=medium, or ≥3=high).
Pulmonary hypertension	A binary indicator for whether the beneficiary had a diagnosis code for pulmonary hypertension on at least one inpatient, or outpatient claim that occurred during the baseline period
Gastroesophageal reflux disease (GERD)	A binary indicator for whether the beneficiary had a diagnosis code for gastroesophageal reflux disease on at least one inpatient, or outpatient claim that occurred during the baseline period
Asthma	A binary indicator for whether the beneficiary had a diagnosis code for asthma on at least one inpatient, or outpatient claim that occurred during the baseline period
Sleep apnea	A binary indicator for whether the beneficiary had a diagnosis code for obstructive sleep apnea on at least one inpatient, or outpatient claim that occurred during the baseline period
Lung biopsy	A binary indicator for whether the beneficiary had a diagnosis or procedure code for a lung biopsy on at least one inpatient, or outpatient claim that occurred during the baseline period
HRCT scan	A binary indicator for whether the beneficiary had a procedure code for a high-resolution computerized tomography scan on at least one inpatient, or outpatient claim that occurred during the baseline period
Oxygen	A binary indicator for whether the beneficiary had a diagnosis, procedure revenue center code for oxygen therapy or supplemental oxygen on at least one inpatient, outpatient, skilled nursing facility, home health or durable medical

NIS Protocol Page 21 of 36

Variable Description		
	equipment claim that occurred during the baseline period	
Pulmonary rehabilitation	A binary indicator for whether the beneficiary had a procedure or revenue center code for pulmonary rehabilitation services on at least one inpatient, outpatient, skilled nursing facility, home health or durable medical equipment claim that occurred during the baseline period	
Ventilator use	A binary indicator for whether the beneficiary had a diagnosis or procedure code for ventilator use on at least one inpatient, or outpatient claim that occurred during the baseline period	
COPD	A binary indicator for whether the beneficiary had a diagnosis code for chronic obstructive pulmonary disease on at least one inpatient, or outpatient claim that occurred during the baseline period	
Нурохіа	A binary indicator for whether the beneficiary had a diagnosis code for hypoxia on at least one inpatient, or outpatient claim that occurred during the baseline period	
Pharmacy use and spending		
Medication count	The count of the number of unique outpatient prescription medications for which beneficiary has pharmacy claims during the baseline period	
Total pharmacy spending	A continuous, non-negative variable representing the total amount paid by all parties for outpatient prescription medications as reported in pharmacy claims during the baseline period.	
OOP pharmacy spending	A continuous, non-negative variable representing the total amount paid out-of-pocket by the beneficiary for outpatient prescription medications as reported in pharmacy claims during the baseline period.	
Inpatient hospitalization use and spending		
Any inpatient stay	A binary indicator for whether a beneficiary had at least one inpatient hospitalization for any cause during the baseline period.	

NIS Protocol Page 22 of 36

Variable	Description	
Inpatient stay count	A count of the number of inpatient hospitalizations for any cause a beneficiary had during the baseline period.	
Inpatient length of stay	A count of the number of days (length of stay) a beneficiary was hospitalized in an inpatient facility during the baseline period. Length of stay for each inpatient hospitalization claim will be calculated as the arithmetic difference between each claim's from and through dates.	
Total inpatient spending	A continuous, non-negative variable representing the total amount paid by all parties for all inpatient hospitalizations (for any cause) as reported in inpatient facility claims during the baseline period.	
Outpatient facility use and spending		
Any outpatient visit	A binary indicator for whether a beneficiary had at least one claim for services provided by an outpatient facility for any cause during the baseline period.	
Outpatient visit count	A count of the number of unique dates with an outpatient facility for any cause claim a beneficiary had during the baseline period.	
Total outpatient spending	A continuous, non-negative variable representing the total amount paid by all parties for outpatient facility claims during the baseline period.	
Medical spending		
Total Medical spending	A continuous, non-negative variable representing the total amount paid by all parties all medical claims during the baseline period, calculated as the sum of the allowed amounts on each claim.	
OOP Part B spending	A continuous, non-negative variable representing the total amount paid out-of-pocket by the beneficiary for all medical claims during the baseline period.	
Total spending		
Total spending	A continuous non-negative variable representing the total amount paid by all parties for all medical	

NIS Protocol Page 23 of 36

Study number: 1199-0526 Document number: c41847952-01

Proprietary confidential information © 2023	Boehringer Ingelheim International	I GmbH or one or more of its affiliated companies

Variable	Description	
	and pharmacy claims during the baseline period and will be calculated as the sum of total pharmacy and total medical spending.	
Other use		
Any ED visit	A binary indicator for whether a beneficiary had at least one emergency department visit during the baseline visit.	
ED visit count	A count of the number of unique dates with an emergency department visit that a beneficiary had during the baseline period.	
Any pulmonology visit Any pulmonology visit A binary indicator for whether a benefic treated by a specialist in pulmonary dise the baseline period. Treatment by a pulmonologist will be identified by the pof a pulmonary specialty code in inpatie outpatient claims.		
Pulmonology visit count	A count of the number of unique dates with treatment by a specialist in pulmonary disease that a beneficiary had during the baseline period.	

9.4 DATA SOURCES

As described above in Section 9.2.1, We will use administrative health insurance claims data from the Optum Research Database (ORD) for the period of October 1, 2013 through end of data availability (September 30, 2022). The ORD contains enrollment information, as well as fully-adjudicated medical claims and pharmacy claims for commercial enrollees and MAPD beneficiaries. In 2018, the ORD included 14.3 million commercial enrollees with medical and pharmacy benefits and 4.3 million beneficiaries with Medicare Part C (commonly referred to as the Medicare Advantage program).

9.5 STUDY SIZE

As this is a descriptive study, no formal calculation of sample size was performed. In a preliminary feasibility analysis using Optum data to examine sample size, we have found that 1,979 patients newly initiated pirfenidone, and 2,559 patients who initiated nintedanib between 10/2014 to 12/2020. As such, this study is expected to have a sufficient sample.

NIS Protocol Page 24 of 36

Study number: 1199-0526 Document number: c41847952-01

Proprietary confidential information © 2023 Boehringer Ingelheim International GmbH or one or more of its affiliated companies

9.6 DATA MANAGEMENT

Data cleaning and analysis will be executed by US HEOR group. Paper printouts of the data are not required and will not be produced. Study documents, including synopsis, protocol, final results, and publications, will be archived on the BIRDS (Boehringer Ingelheim Regulatory Documents for Submission).

9.7 DATA ANALYSIS

9.7.1 Main analysis

Baseline characteristics for the pirfenidone and nintedanib cohorts will be reported as frequencies with percentages for categorical data, and means with standard deviations (SD), and median with interquartile range will be reported for continuous variables. We will compare the baseline characteristics using Student's T-test or Wilcoxon rank-sum test for continuous variable, and chi-square test for categorical variable

Average daily dose during first 6 months and 12 months after drug initiation will be reported as means with standard deviations (SD), and median with interquartile range. Six months and 12-months daily dose categories will be presented as frequencies with percentages. Incidence of dose reduction will be reported by month of occurrence (using month 2 and onwards) and reported as frequencies with percentages. Time to drug dose reduction will be reported in months (mean (SD)). Drug discontinuation will be reported as frequencies with percentages, and time to drug discontinuation will be reported in months (mean (SD)). As this is a descriptive study, there will be no multivariable adjustment and/or direct comparison of outcomes between the pirfenidone and nintedanib cohort.

9.7.2 Post-hoc analysis

As this study is a descriptive analysis, no adjustments or direct comparison between pirfenidone and nintedanib cohort is proposed a-priori. If significant differences in the baseline characteristics between the pirfenidone and nintedanib cohorts are observed, we propose to conduct propensity score matching (PSM) to balance the baseline characteristics between the two cohort. Specifically, pirfenidone initiators will be matched to nintedanib initiators using the technique of nearest neighbor match on an estimated propensity score (caliper width of ±0.001 unit). The propensity score for this analysis will be obtained from a logistic regression model using pre-index measures to predict the probability of being in the pirfenidone initiator cohort. Pre-index measures which will be included are demographic (age, sex, census region, index year), clinical (CCI, pulmonary hypertension, COPD, asthma, GERD, HRCT scan, oxygen use, and ventilator use), and healthcare utilization measures (total pharmacy spend, total medical spend, number of pulmonology visits)

We will compare differences in baseline characteristics between the pirfenidone and nintedanib cohorts before and after propensity score matching. The success of the propensity score-matching to reduce confounding will be assessed by evaluating the standardized differences in the covariates between the study groups after matching. For each covariate, the standardized difference percent (di) will be calculated as: $di = 100 * (xi - xni) / \sqrt{(s2i + xni)}$

NIS Protocol Page 25 of 36

Study number: 1199-0526 Document number: c41847952-01

Proprietary confidential information © 2023 Boehringer Ingelheim International GmbH or one or more of its affiliated companies

s2ni}/2) where xi and xni are the sample means of the ith covariate in the pirfenidone and nintedanib cohorts, respectively, and s2i and s2ni are the corresponding sample variances. A standardized difference of <10% is considered an acceptable level of difference (or supports the assumption of balance) between the comparison groups.

We will reassess the primary and secondary outcomes in the matched cohorts (see Section 9.7.1 for more details)

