Variables:	The main outcome of our study will be incidence of dose reduction/interruption, calculated separately for nintedanib and pirfenidone. For each patient, average daily dose will be calculated in pre-specified time-periods (for example – the first 6 months, the first 12 months, and the average daily dose calculated separately in each month since drug initiation). Incidence of dose reduction/interruption will be defined as average daily dose not following the prescribing information.		
	As a secondary outcome, we will also assess drug discontinuation during first 6 and 12 months separately for pirfenidone and nintedanib and will be defined as a gap of at least 60 days in filling of prescription (a gap of 60 days after the prescription date + days of supply for the current prescription).		
Data sources:	We will use administrative health insurance claims data from the Optum Research Database (ORD) for the period of October 1, 2013 through end of data availability (currently September 30, 2022). This database was chosen as it includes claims of Medicare Advantage and commercially enrolled beneficiaries.		
Study size:	As this is a descriptive study, no formal calculation of sample size was performed. In a preliminary feasibility analysis using Optum data to examine sample size, we have found that 1,979 patients newly		

NIS Protocol Page 9 of 36

Name of company:			
Boehringer Ingelheim			
Name of finished medicinal product: Nintedanib (Ofev) and Pirfenidone (Esbriet)			
Name of active ing Nintedanib (Ofev) : Pirfenidone (Esbrie	and		
Protocol date:	Study number:	Version/Revision:	Version/Revision date:
24 MAR 2023	1199-0526		
	initiated pirfenidone, and 2,559 patients who initiated nintedanib between 10/2014 to 12/2020. As such, this study is expected to have a sufficient sample.		

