9.2 SETTING

9.2.1 Study sites

We will use administrative health insurance claims data from the Optum Research Database (ORD) for the period of October 1, 2013 through end of data availability (currently September 30, 2021). The ORD contains enrollment information, as well as fully-adjudicated medical claims and pharmacy claims for commercial enrollees and MAPD beneficiaries. In 2018, the ORD included 14.3 million commercial enrollees with medical and pharmacy benefits and 4.3 million beneficiaries with Medicare Part C (commonly referred to as the Medicare Advantage program). Medicare Advantage beneficiaries choose to receive all of their health care services through a provider organization in lieu of Medicare Part A/B coverage (commonly referred to as Medicare Fee for Service). These plans are referred to as MAPD when combined with Medicare Part D coverage. The average enrollment duration was 31.4 and 37.3 months for commercial enrollees and MAPD enrollees, respectively. Underlying information is geographically diverse across the United States and enrollees are fairly representative of the U.S. population. Medicare beneficiaries retain a single identifier within the system and can be tracked as they change plans, or as they disenroll and reenroll over time.

Claims for pharmacy services are typically submitted electronically by the pharmacy at the time prescriptions are filled. The claims history is a profile of all outpatient prescription pharmacy services provided and covered by the health plan. Pharmacy claims data include drug name, dosage form, drug strength, fill date, days of supply, financial information, and de-identified patient and prescriber codes, allowing for longitudinal tracking of medication refill patterns and changes in medications. Pharmacy claims are typically added to the research database within six weeks of dispensing.

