9.2.2 Study population

For the primary study objective, patients included in the cohort need to meet the following criteria:

- Presence of at least one pirfenidone or nintedanib prescription during the identification period (the date of first prescription for pirfenidone/nintedanib is the index date)
- Evidence of IPF: patient with at least one inpatient or two outpatient claims (>14 days apart) with a diagnosis code for IPF (ICD-10-CM: J84.112; ICD-9-CM: 516.31) during the study period (10/01/2013 to 09/30/2022)
- At least 18 years old at the index date
- Have at least 12 months of continuous enrollment in the health plan during pre-index period, and at least 6 months of continuous enrollment in post-index period (for 12-months analysis, patients would be required to have 12 months post-index continuous enrollment)

Exclusion criteria include the following:

- Any history of lung transplant during the 12-months pre-index/baseline period
- Any claims for a skilled nursing facility, a long-term care facility or hospice care during the 12-month pre-index period
- Evidence (≥2 ICD-9-CM or ICD-10-CM diagnostic codes on different dates) of non-IPF chronic fibrosis ILD or connective tissue diseases during the 12-months pre-index period. The following conditions will be excluded: autoimmune, or connective tissue diseases (i.e., rheumatoid arthritis (RA), systemic lupus erythematosus (SLE), dermatopolymyositis, systemic sclerosis, Sjogren's syndrome, and mixed connective tissue disease (CTD)), sarcoidosis, and hypersensitivity pneumonitis).
- Missing demographic information (i.e., age or sex)

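### Insurance type (commercial or Medicare Advantage) is in neither the baseline table nor the propensity model, so a payer imbalance between the cohorts would go unseen

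*Combined protocol and SAP*

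**What the plan says.** The Abstract gives the payer mix as the reason for using this database: "This database was chosen as it includes claims of Medicare Advantage and commercially enrolled beneficiaries". Section 9.2.1 then describes the two groups separately, by size ("In 2018, the ORD included 14.3 million commercial enrollees with medical and pharmacy benefits and 4.3 million beneficiaries with Medicare Part C") and by length of cover ("The average enrollment duration was 31.4 and 37.3 months for commercial enrollees and MAPD enrollees, respectively").

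In 9.3.3, the block headed "Demographic and socioeconomic characteristics" holds age, sex, census region and index year. The later blocks cover clinical conditions, pharmacy, inpatient, outpatient, medical and total spending, and other use. None has a payer or plan-type row.

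Section 9.7.2 makes matching conditional on significant baseline differences between the cohorts. It lists the model terms in three groups. The first is "demographic (age, sex, census region, index year". The second holds eight clinical terms: a comorbidity score, four diagnoses and three markers of work-up or support. The third is "healthcare utilization measures (total pharmacy spend, total medical spend, number of pulmonology visits". Balance is accepted when the standardized difference is below 10%, and the outcomes are then reassessed in the matched cohorts.

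Section 9.9 mentions insurance cover only as a limit on generalizability.

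**The concern.** Both outcomes are built from pharmacy fills, and eligibility depends on staying enrolled: 12 months before index and "at least 6 months of continuous enrollment in post-index period" (12 months for the 12-month analysis). Cover could plausibly bear on both. A payer difference between the pirfenidone and nintedanib cohorts is therefore something a reader would want to see, and the plan has no place where it would show.

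Three safeguards depend on the listed covariates: the baseline comparison, the trigger for matching, and the balance check. A variable absent from the list is outside all three. If matching is run, the report could state that the cohorts are balanced while they still differ by payer. The results are likely to be read side by side, because Section 7 says the study may show decision makers how dosing complexity differs between the two drugs.

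**Working it through.** **1. Are the lists complete without payer?** The propensity model has 4 demographic, 8 clinical and 3 utilization terms, 15 in all. None is insurance type. The 9.3.3 table has none either. Its row labelled as out-of-pocket Part B spending is defined over all medical claims, so it does not mark Medicare cover. The omission is confirmed.

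**2. What do the documents show about the two payers?**
- Enrolment: 37.3 − 31.4 = 5.9 months; 5.9 / 31.4 = 18.8% longer in Medicare Advantage.
- Share of the 2018 database: 4.3 / (14.3 + 4.3) = 23.1% Medicare Advantage.
- Illustration only, assuming exponential enrolment times, which the documents do not state: P(T ≥ t) = exp(−t / mean).
  - 18 months (12 + 6): exp(−18/31.4) = 56.4% commercial; exp(−18/37.3) = 61.7% Medicare Advantage.
  - 24 months (12 + 12): exp(−24/31.4) = 46.6%; exp(−24/37.3) = 52.5%.

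Under that assumption, the enrolment rule would change the payer mix of the sample, and again between the 6- and 12-month analyses. It says nothing about payer and drug choice.

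**3. What imbalance would the plan's own limit flag, if payer were listed?** For a binary variable the 9.7.2 formula is d = 100 × (p1 − p2) / √{[p1(1 − p1) + p2(1 − p2)] / 2}. The Medicare Advantage share among IPF initiators is not given, so a range is assumed.
- Overall share 50%: p1 = 0.525, p2 = 0.475, d = 100 × 0.050 / 0.4994 = 10.0%.
- Overall share 80%: p1 = 0.82, p2 = 0.78, d = 100 × 0.040 / 0.3995 = 10.0%.

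A gap of about 4 to 5 percentage points would breach the limit. As written, it would not be tested.

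**4. How large could the effect on a matched contrast be?** Shift = residual payer gap × outcome difference between payers. Both inputs are assumptions.
- Gap of 10 to 20 points, outcome difference of 10 points: 0.10 × 10 = 1 point; 0.20 × 10 = 2 points.
- Gap just at the 10% limit (4 to 5 points), same outcome difference: 0.4 to 0.5 points.

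**5. Against what precision?** Take 30% (assumed) and 1,979 per group, the smaller feasibility count in 9.5, treating the groups as independent.
- Half-width for a difference: 1.96 × √(2 × 0.3 × 0.7 / 1979) = 2.9 points.
- Half-width for one proportion: 1.96 × √(0.3 × 0.7 / 1979) = 2.0 points.

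A shift in a two-cohort contrast belongs against the first. So 1 to 2 points is about 35% to 70% of the half-width (1/2.86 and 2/2.86).

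**The case against.** The strongest reply is that nothing here demonstrates confounding. The 31.4 and 37.3 months are database-wide averages without standard deviations, not figures for IPF antifibrotic initiators. The enrolment rule is the same for both cohorts, so it distorts a drug contrast only if payer mix also differs by drug, and no figure in the documents bears on that. A reader might infer from the enrolment gap that payer confounds the comparison; the documents do not support that step. This part of the reply stands.

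It is also true that the main analysis reports each drug separately, unadjusted and without direct comparison. Its proportions, as descriptions of the enrolled patients, are not biased by leaving payer out. Matching is conditional, and 9.7.2 sends the matched outcomes back to the methods of 9.7.1, which exclude direct comparison, so no formal matched contrast is specified. This stands too, although matched results will be hard to read any other way than side by side.

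Age and spending, both in the model, may carry part of the payer difference. A residual gap of 20 points after matching on them is a high assumption. The spending terms in the model are totals across all parties rather than out-of-pocket amounts, so an argument from differing benefit design has little force against them.

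The reply does not remove the omission itself: no listed variable identifies cover, and partial proxies do not let anyone check it.

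**Conclusion.** The point holds as a gap in reporting and in the balance check, not as a demonstrated bias. Insurance type is missing from both lists, and a payer imbalance could neither be seen at baseline, nor trigger matching, nor fail the balance limit. The missing baseline row applies whatever happens; the missing model term matters only if matching is run.

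The size is conjectural. A shift of 1 to 2 points needs a residual payer gap of 10 to 20 points and a 10-point outcome difference between payers, neither of which is in the documents. It would be smaller if age and spending act as proxies. A reader might set it against the 2.0-point half-width of a single proportion and conclude that bias matches sampling error. The comparable figure is about 2.9 points. It would be wider still if the ±0.001 caliper drops pairs or if the 9.2.2 criteria reduce the feasibility count, since 9.5 does not say whether they were applied.

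This is a nearly free improvement rather than a flaw that threatens the study's results.

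**What to change.** - Add insurance type at index (commercial or Medicare Advantage) to the demographic block of 9.3.3, so that it is reported and compared with the other baseline characteristics and can count towards the decision to match.
- If matching is run, include it in the propensity model and in the standardized-difference check in 9.7.2.

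The cost is one derived variable. Sex and census region are already taken from the enrolment record covering the index date. That this record also carries payer is an inference, but a reasonable one, since 9.2.1 gives counts and enrolment duration by payer. Cohorts, outcome definitions and the descriptive analysis stay as they are. Outcome tables split by payer are not needed for this point; they would be an optional subgroup analysis.

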9.9 LIMITATIONS OF THE RESEARCH METHODS

Several potential limitations of this study are discussed below:

- This study is based on healthcare claims data, daily dose calculations derived from monthly pharmacy fills may not represent the actual daily intake of the patient
- We could not ascertain reasons for discontinuations and/or dose reduction in this study, as adverse events may not be reliably captured in the claims database, and also the reasons for drug discontinuation are not captured in the claims database
- We will not be able to distinguish between dose reduction vs. temporary dose interruption for a patient, as the main outcome is based on calculation of daily dose based on pharmacy claims
- Due to lack of availability of laboratory data and clinical information (for example FVC% at baseline), severity of IPF, and results of the laboratory tests will not be

NIS Protocol Page 26 of 36

Study number: 1199-0526 Document number: c41847952-01

Proprietary confidential information © 2023 Boehringer Ingelheim International GmbH or one or more of its affiliated companies

observed. The severity of IPF may influence the initiation, discontinuation, and dose-reduction of an anti-fibrotic agents

• This study cannot be generalized to the entire U.S. population. ORD only covers patients with commercial insurance or Medicare Advantage plan. The findings of this study may not be applicable for patients with public insurance such as Medicare Fee-For-Service or without insurance.

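### The conditional propensity-score model (9.7.2) omits severity-related baseline measures that 9.3.3 already derives, so adjustment in the matched re-analysis is less complete than the data allow

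*Combined protocol and SAP*

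**What the plan says.** Section 9.7.2 makes matching conditional. It is done only if the pirfenidone and nintedanib cohorts differ significantly at baseline, and its purpose is to balance those characteristics. The score comes from a logistic model with three groups of terms:

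- Demographic: "Pre-index measures which will be included are demographic (age, sex, census region, index year".
- Clinical: "clinical (CCI, pulmonary hypertension, COPD, asthma, GERD, HRCT scan, oxygen use, and ventilator use".
- Utilization: "healthcare utilization measures (total pharmacy spend, total medical spend, number of pulmonology visits".

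Matching is nearest-neighbour within a caliper of ±0.001. Baseline characteristics are then compared before and after matching. On the balance measure the section says "For each covariate, the standardized difference percent (di) will be calculated as", and values below 10% are acceptable. The primary and secondary outcomes are reassessed in the matched cohorts.

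Section 9.3.3 defines a longer set of baseline variables. It includes an indicator for patients who "had a diagnosis code for hypoxia on at least one inpatient" or outpatient claim, and one for a "procedure or revenue center code for pulmonary rehabilitation services". It also defines inpatient stay count, length of stay and ED visit count. None of these is in the model.

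Section 9.9 lists unobserved IPF severity (no FVC, no laboratory results) as a limitation and adds: "The severity of IPF may influence the initiation, discontinuation, and dose-reduction of an anti-fibrotic agents".

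**The concern.** When the direct measure of severity is missing, the usual remedy is to adjust for whatever the data hold that tracks it. A hypoxia diagnosis, referral to pulmonary rehabilitation, hospital stays and ED visits are plausible markers of that kind, and the study derives them anyway. Leaving them out means that nothing in the matching directly acts on them.

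The trigger and the model also do not correspond. Matching starts from significant differences in baseline characteristics, which 9.7.1 tests without limiting them to the 15 modelled measures. A significant difference in hypoxia or length of stay could therefore set off a matching that uses neither.

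At stake is the credibility of the matched outcome results. A difference that remained between the cohorts might partly reflect how sick the patients were at initiation.

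**Working it through.** **1. Set comparison.** The variables in 9.3.3 were counted by block and checked against the list in 9.7.2.

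| Block in 9.3.3 | Defined | In the model |
|---|---|---|
| Demographic | 4 | 4 |
| Clinical | 12 | 8 |
| Pharmacy | 3 | 1 (total spend) |
| Inpatient | 4 | 0 |
| Outpatient facility | 3 | 0 |
| Medical spending | 2 | 1 (total spend) |
| Total spending | 1 | 0 |
| ED | 2 | 0 |
| Pulmonology | 2 | 1 (visit count) |
| **Sum** | **33** | **15** |

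So 33 − 15 = 18 variables are left out. The four clinical ones are hypoxia, pulmonary rehabilitation, lung biopsy and sleep apnea. No inpatient or ED variable enters as such.

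**2. What the model already holds.** Oxygen use, ventilator use, pulmonary hypertension and pulmonology visit count all bear on respiratory severity. Total medical spend sums allowed amounts over all medical claims, so admissions and ED visits enter it as cost. A cost total cannot separate acute admissions from other expensive care.

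**3. Whether sample size explains the short list.** Section 9.5 makes no sample-size calculation, so there is no planned figure to reproduce. It gives feasibility counts of 1,979 pirfenidone and 2,559 nintedanib initiators.

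- Parameters now: age 1, sex 1, region 3, index year 7 (eight calendar years), CCI 1 (continuous), binary clinical terms 7, utilization 3. Sum: 23.
- With hypoxia, rehabilitation, one inpatient measure and ED count: 23 + 4 = 27.
- Smaller cohort: 1,979/23 = 86 patients per parameter now and 1,979/27 = 73 after.
- If only about half (990) met the eligibility criteria, an assumption: 990/23 = 43 and 990/27 = 37.

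The model can carry the extra terms. This says nothing about how many patients would find a match.

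**4. Illustrative size.** The documents give neither the prevalence of these markers nor their link to the outcomes. For one omitted binary marker with prevalence p and residual standardized difference d, using a common variance:

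- prevalence difference = d × √(p(1 − p))
- shift in the outcome contrast = prevalence difference × risk difference of the outcome between patients with and without the marker

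Assume p of 20% to 40% and a risk difference of 10 to 30 points, taken as what remains after the modelled covariates.

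- d = 10%, low end: 0.10 × √(0.2 × 0.8) = 0.040, and 0.040 × 10 = 0.4 points.
- d = 10%, high end: 0.10 × √(0.4 × 0.6) = 0.049, and 0.049 × 30 = 1.5 points.
- d = 30%, low end: 0.120 × 10 = 1.2 points.
- d = 30%, high end: 0.147 × 30 = 4.4 points.

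All of these inputs are assumptions. The range shows scale only and is not an estimate for this study.

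**The case against.** The case for leaving the plan alone has several parts, and most of them limit the point.

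- **Severity is not named as a confounder of drug choice.** A reader might infer from 9.9 that the plan admits confounding by severity between the drugs. The sentence speaks of starting, stopping and reducing an antifibrotic. It does not say that severity steers patients to one drug over the other, and everyone in both cohorts is an initiator. Differential severity is a reasonable worry, but the documents do not state it.
- **The model is not blind to severity.** Oxygen and ventilator use are at least as direct as the omitted markers. This stands, and it makes the gap a partial one.
- **Omitted variables are not left wholly unbalanced.** Matching on oxygen use will tend to bring hypoxia closer too. This stands, but the help is partial and not assured.
- **The 18-of-33 count overstates the gap.** Total spending is pharmacy plus medical spending, and any pulmonology visit follows from the visit count. Lung biopsy may reflect diagnostic work-up, and sleep apnea and medication count are weak severity markers. The case therefore rests on hypoxia, rehabilitation, inpatient use and ED use.
- **The balance check is a safeguard.** If it covers every variable in 9.3.3, it would reveal leftover imbalance. The wording does not settle whether it reaches beyond the model, and no action is stated when a variable fails.
- **The analysis is conditional and secondary.** This stands and caps the importance of the point.

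**Conclusion.** The point holds as incomplete adjustment in the conditional matched re-analysis. The model leaves out hypoxia, pulmonary rehabilitation, inpatient use and ED visits without a reason, although the study derives them and the matching is meant to balance baseline characteristics. The feasibility counts offer no ground for the omission.

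It does not follow that the matched results would be biased by a known amount. The 0.4 to 4.4 point range rests wholly on assumed inputs. Nor does the point touch the primary and secondary aims, which describe each cohort separately without adjustment or direct comparison. Adding the variables would reduce possible residual confounding by severity but could not remove it, because FVC stays unobserved.

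**What to change.** In 9.7.2, add to the propensity model:

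- hypoxia;
- pulmonary rehabilitation;
- one inpatient-use measure (stay count or length of stay);
- ED visit count.

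State that post-matching standardized differences will be reported for all 33 variables in 9.3.3, in or out of the model, against the 10% criterion. A sentence on what follows when a variable fails would close the remaining gap.

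No new data are needed, since every variable is already defined for the baseline tables. The cost is a possibly smaller matched sample: more predictors can separate the scores further, and the ±0.001 caliper is narrow. The loss cannot be estimated from the documents, so the number matched in each cohort should be reported beside the matched results.
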